#### Allocation Strategy

Participants will be randomized at 1:1 ratio into Group A or B. Randomization will be stratified by states and by various block sizes. The randomization will be carried out via the Clinical Trial Conduct (CTC) website (<https://biostatistics.mdanderson.org/ClinicalTrialConduct>) which is housed on a secure server at MD Anderson and maintained by the MD Anderson Department of Biostatistics. Access to the website will be gained through usernames and passwords provided by the MD Anderson Department of Biostatistics. Training on the use of the CTC will be provided by the biostatistical collaborator of the study before the study activation.

#### Analysis plan

Patients' demographic characteristics at baseline will be summarized using descriptive statistics such as mean, standard deviation, median, interquartile range (IQR), and frequency where appropriate. We will apply Student t-test/Wilcoxon test and Kruskal-Wallis test/analysis of variance (ANOVA) to compare continuous variables between arms, and the chi-square test or the Fisher's exact test to assess the differences of categorical variables between arms.[16]

As primary analysis, we will perform two-sided two group t-test to compare the differences of the three primary endpoints between the two arms. We will perform similar analysis on knowledge scores. For these efficacy endpoints, intend-to-treat analysis will be applied to the participants. We will look at the impact of race/ethnicity (African American vs. Caucasian) on the relationship between the outcomes and lung cancer screening materials using general linear regression. We will also assess the interaction between intervention and race/ethnicity using linear regression model to examine whether or not the decision aid has differential effects between African Americans and Caucasians by testing.

We will use two-sided two group t-test to compare the change of knowledge scores from baseline to post intervention between the two arms. Since the knowledge outcome will be assessed at week 1 and then 3-month and 6-month follow-ups, linear mixed effect models for longitudinal measures[17] will be employed to assess the change in the magnitude of the outcomes over time adjusting for multiple covariates including intervention indicator, age, gender, race, education level, insurance status, and other factors. We may also look at the interaction between intervention and time. Appropriate transformation of the measures will be used in the analyses to satisfy the normality assumption of linear mixed effect model. Mode of administration and completion of intervention/control materials (i.e., dose/exposure) will be tracked to account for their

effects.

We will also estimate the lung cancer screening rate within each arm along with 95% confidence interval. Chi-square test will be used to assess the differences of the lung cancer screening rates between arms.

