### **4.0 Research Plan and Methods**

The design for this study is a randomized trial with quitline patients recruited through state-based quitlines. Patients will be randomly assigned to the patient decision aid (200 patients) or standard educational information about lung cancer screening (200 patients). (Note that based on our estimates of attrition, up to 550 patients may be enrolled in the study to achieve a final sample of 400.) The design includes a pre-test assessment with a subscale of the knowledge measure developed for this study, an assessment at 1-week to collect data on the outcomes for the study and a 3-month follow-up to determine how well patients retain the information and track any use of screening services. A 6-month follow-up assessment will also be conducted on a subsample of the patients to track lung cancer screening rates via patient report.

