#### Eligibility Assessment, Informed Consent, and Randomization

Patients with an interest in the study will be given information to contact the research team about participation. Research staff will provide a description of the study using a recruitment script (appendix I) and assess the patients' eligibility following the study eligibility criteria using a screening form (appendix J). These forms will be kept for all individuals screened including screen-failures and used for aggregate reporting of eligibility. We propose to collect informed consent from patients via telephone. See Section 7 for details about the verbal consent process and request for waiver of written authorization for the study. Contact information (appendix I) and patient characteristics (see baseline survey in appendix K) will be collected at that time. Eligible, consented patients will then be allocated to receive the patient decision aid or standard educational materials using the procedure described under "Allocation Strategy." Randomization will be done within each state organization (i.e., pre-stratification by state quitline) to control for any systematic differences in clients served.

Patients will be mailed the study materials for review. Patients will be instructed to review the materials – patient decision aid or standard educational materials – over the following week. A link to the current patient decision aid and standard educational materials can be found in appendix L. Because the patient decision aid is a video, during the eligibility assessment we will ask patients if they have access to a DVD player or computer with a DVD drive for viewing the aid. We will also make the aid available for viewing on the Internet. If patients do not have access to a DVD player or have Internet access, we will facilitate their finding access locally (e.g., public libraries). In the data analysis phase, we will examine any differences in the study outcomes across the different modes for delivering the decision aid and adjust for these as needed.

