## **5.0 Statistics and Justification of Sample Size**

### Justification of Sample Size

The primary analysis will be to compare three primary outcomes, i.e., Preparation for Decision Making Scale, informed subscale (IS) and values subscale (VS) of Decisional Conflict Scale (DCS), between patients who were randomized to the patient decision aid arm (Arm 1) and those who were randomized to the standard educational materials (Arm 2). We specifically chose the IS and VS subscales because two of the International Patient Decision Aid Standards criteria for decision aids are that the aid helps individuals feel informed and clear about values. Since the three primary endpoints are equally of significance, to control overall type I error rate at a significant level of 0.05, we will compare each of the three primary outcomes at a significant level of 0.017 (0.05/3) using Bonferroni multiple comparison adjustment.

Based on results from other decision aid trials using the DCS, we estimate Arm 2 will have a mean DCS IS or VS score of 30 while Arm 1 will have a mean DCS IS or VS of 25.[15] A sample size of 190 in each arm will have 80% power to detect a difference in means of 5 using a two group t-test with a 0.017 two-sided significance level assuming a common standard deviation (SD) of 15 on IS or VS.[15] We calculated the effect size the study would be able to detect with the given sample size for preparation for decision making because we had limited preliminary data for this measure. A sample size of 190 in each arm will have 80% power for the study to detect an effect size of 0.332 using a two group t-test with a 0.017 two sided significance level.

As a secondary analysis, we will also compare the difference of knowledge scores between the two arms using two-sided two group t-test. We hypothesize that Aim 2 scores to be 50 (half the knowledge questions answered correctly) with a SD of 19.36.[12] We further expect, based on our pilot study, the knowledge scores for Aim 1 to have a SD of 15.76.[12] If we randomize 380 participants 1:1 to each of the two arms, we would have 88% power to detect a difference in knowledge scores of 5.75 (50 vs. 55.75) using a two-sided two-sample t-test with unequal variances and alpha of 0.05. Therefore, the target final sample for the study will be 400 patients (200 per study arm). With an anticipated retention rate of 80% by the 3-month follow-up, 550 patients will be recruited for the study.

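### The unadjusted primary t-tests are valid and correctly sized, but a pre-specified linear model using state and baseline data already collected could add some power at little cost

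*Combined protocol and SAP*

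**What the plan says.** The primary outcomes are the Preparation for Decision Making Scale and the informed (IS) and values (VS) subscales of the Decisional Conflict Scale (DCS), all administered at the 1-week follow-up. The Analysis plan in section 5.0 says of them: "As primary analysis, we will perform two-sided two group t-test to compare the differences of the three primary endpoints between the two arms". No covariate and no term for state is named.

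The sample size rests on the same test. Under Justification of Sample Size, "we will compare each of the three primary outcomes at a significant level of 0.017 (0.05/3) using Bonferroni multiple comparison adjustment", and "A sample size of 190 in each arm will have 80% power to detect a difference in means of 5 using a two group t-test", "assuming a common standard deviation (SD) of 15 on IS or VS".

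Baseline information is available. Section 4.0 says: "The design includes a pre-test assessment with a subscale of the knowledge measure developed for this study". The subsection on eligibility, consent and randomization says that "patient characteristics (see baseline survey in appendix K) will be collected at that time", and places allocation after that step. It also says why randomization is stratified by state quitline: the clients served may differ systematically.

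The only multi-covariate model in the plan is the longitudinal one for knowledge, with terms "including intervention indicator, age, gender, race, education level, insurance status, and other factors". Separately, the plan has a race/ethnicity regression on the outcomes, with an interaction test, and conditional adjustment for how the decision aid was delivered.

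**The concern.** How informed, clear or prepared a person feels a week after receiving the materials may vary with prior knowledge, education and similar characteristics. Any such variation stays in the error term of a plain t-test. The plan already treats age, gender, race, education and insurance as worth adjusting for when knowledge is the outcome in the same patients, but does not use them in the tests on which the trial's conclusion rests. State is in the design and absent from the primary analysis.

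The calculation for the two DCS subscales has almost no slack at 190 per arm. For Preparation for Decision Making, the plan concedes limited preliminary data and gives only a detectable effect. In a randomized trial, a linear model with pre-specified baseline covariates estimates the same mean difference as the t-test and preserves the type I error. The stake is precision only: a few points of power and slightly narrower intervals, if the covariates are related to the outcomes.

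**Working it through.** **Inputs from Justification of Sample Size:** 190 per arm; IS or VS means of 30 and 25 (difference 5); SD 15; two-sided level 0.017; target 200 per arm.

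**Assumptions, not in the documents:** R², the share of within-arm outcome variance explained by the covariates, from 0 to 0.15; and the number of covariate terms k, 6 or 10. Six counts one term for each of baseline knowledge, age, gender, race, education and insurance. Ten allows several indicators for the categorical ones. State terms are extra.

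**Step 1: the plan's own figure.**
- Standard error = 15 × √(2/190) = 1.539.
- Noncentrality = 5 / 1.539 = 3.249, with 378 degrees of freedom and critical t = 2.397.
- Power = 80.2%, against 80% stated.
- The noncentral t needs 189.03 per arm for 80% power, so 190.
- The detectable effect at 190 per arm is 0.3325 SD, against 0.332 stated.

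The sample size is reproduced for the unadjusted test.

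**Step 2: the adjusted model.**
- Residual SD = 15 × √(1 − R²).
- Noncentrality = 5 / [residual SD × √(2/n)] × √(1 − k/(2n − 2)).
- Degrees of freedom = 2n − 2 − k.

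The last factor in the noncentrality charges for average chance imbalance in the covariates.

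Example, R² = 0.10 and k = 10:
- Residual SD = 15 × √0.90 = 14.23.
- Standard error before the charge = 14.23 × √(2/190) = 1.460.
- Noncentrality = (5 / 1.460) × √(1 − 10/378) = 3.425 × 0.9867 = 3.379.
- With 368 degrees of freedom, power = 83.6%.

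Power at 190 per arm (unadjusted: 80.2%):

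| Assumed R² | Reduced SD only, no charge | 6 terms | 10 terms |
|---|---|---|---|
| 0 | 80.2% | 79.5% | 79.0% |
| 0.02 | 81.1% | 80.4% | 79.9% |
| 0.05 | 82.5% | 81.8% | 81.3% |
| 0.10 | 84.7% | 84.1% | 83.6% |
| 0.15 | 87.0% | 86.3% | 85.9% |

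Shrinking the SD alone overstates power by about 0.6–0.7 points with 6 terms and about 1.1–1.2 points with 10.

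**Step 3: break-even.** The two parts of the noncentrality cancel when R² = k/(2n − 2): 6/378 = 0.016 or 10/378 = 0.026. Below that, adjustment costs a little power.

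**Step 4: target sample.** At 200 per arm, the unadjusted test has 82.5% power. With 6 terms it is 84.0% at R² = 0.05, 86.2% at 0.10 and 88.3% at 0.15.

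**Step 5: state.** The number of states is not given. Counting every term alike, 15 terms in all give 78.4% at R² = 0, 80.7% at 0.05 and about 83% at 0.10, at 190 per arm. This probably overcharges for state, because blocked randomization within state keeps the arms close to balanced on it. Any outcome difference between states would add to R².

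**The case against.** The strongest reply is that nothing is wrong: the trial is sized for a two-group t-test and analysed with one, and preferring a linear model is a choice about efficiency. That stands.

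A reader might go further and infer three things that the documents do not support.

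- *That the baseline variables are prognostic, so primary power is being given away.* No association is reported between any baseline variable and any of the three primary scales. No baseline DCS or Preparation score is described, so the usual strong covariate is absent. With R² of about 0.02 or less, there is little or no gain.
- *That the plan adjusts only the knowledge model.* It also has the race/ethnicity regression on the outcomes and the conditional delivery-mode adjustment. Neither changes the primary test. The first asks about effect modification, and delivery mode of the decision aid is not a baseline covariate common to both arms.
- *That the trial has only 80% power.* That figure belongs to 190 per arm. Recruiting 550 with 80% retention at 3 months gives 440, or 220 per arm, where the unadjusted test has 86.4% power; the primary scales are measured earlier still. At 190 per arm, adjustment with R² of 0.05 adds less than this recruitment margin does.

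Two further cautions stand. The baseline survey's contents are in an appendix that was not available, so the item list is inferred from the knowledge model. The knowledge subscale is called a pre-test, but its timing relative to allocation is not stated outright.

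**Conclusion.** The point holds as a missed efficiency. The primary analysis leaves out the stratification factor and baseline information that could plausibly reduce residual variance. It is not an error of validity or of sample size.

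At 190 per arm with 6 to 10 covariate terms, the change in power runs from a loss of about 1 point (0.7 to 1.2) if the covariates explain nothing, through a gain of 1.1 to 1.6 points at R² = 0.05, to 3.4 to 3.9 points at 0.10 and about 6 points at 0.15. Which of these applies cannot be settled from the documents. The case for adjusting is that the loss is bounded and small, the break-even R² is only about 0.02 to 0.03 before state terms, and a relation with prior knowledge or education above that level is plausible, though not documented.

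**What to change.** In the Analysis plan of section 5.0, before outcome data are seen:

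1. Specify for each 1-week primary score a linear model with arm, state and a closed list of baseline covariates: knowledge subscale, age, gender, race, education level and insurance status, as recorded in the baseline survey. Confirm that each is recorded before allocation.
2. Do not carry over the open-ended last item of the knowledge model's covariate list.
3. Fix the coding of the categorical covariates so that few terms are used and every randomized patient has a category. State how states with few patients are pooled and how missing covariate values are handled.
4. Test the arm coefficient at 0.017, and report the adjusted mean difference with its interval.
5. Keep the two-group t-test as a sensitivity analysis. The sample size justification can stay as it is.

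The cost is wording in the plan, plus at most about 1 point of power for 6 to 10 covariate terms if they explain nothing; many state terms could add somewhat to that. No new data, patients or procedures are needed.

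### Randomisation is stratified by state, but the primary, knowledge and screening-rate tests omit state and no planned analysis names it: a modest, conservative loss of efficiency if states differ

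*Combined protocol and SAP*

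**What the plan says.** Section 4.0 (Eligibility Assessment, Informed Consent, and Randomization) sets the stratification and gives its reason: "Randomization will be done within each state organization (i.e., pre-stratification by state quitline) to control for any systematic differences in clients served". Section 5.0 (Allocation Strategy) repeats it: "Randomization will be stratified by states and by various block sizes". Allocation is 1:1.

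The Analysis plan in section 5.0 then specifies:

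- Three primary endpoints (Preparation for Decision Making, and the informed and values subscales of the Decisional Conflict Scale): "we will perform two-sided two group t-test to compare the differences of the three primary endpoints between the two arms". Knowledge scores get a similar analysis.
- Knowledge change: "We will use two-sided two group t-test to compare the change of knowledge scores from baseline to post intervention between the two arms".
- Screening rate: "Chi-square test will be used to assess the differences of the lung cancer screening rates between arms".

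The sample-size section uses the same unstratified tests. The plan also contains a linear regression with an intervention-by-race/ethnicity interaction and a linear mixed model for knowledge over time, "adjusting for multiple covariates including intervention indicator, age, gender, race, education level, insurance status, and other factors". State is not named in either. Section 4.0 further allows adjustment for the mode of delivering the decision aid as needed.

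**The concern.** When allocation is balanced within strata, differences between strata cancel out of the arm difference. A pooled two-group t-test still counts those differences as random error. If state is prognostic, the reported standard error exceeds the true one, confidence intervals over-cover, and the test rejects less often than its nominal level allows. Each primary endpoint is tested at 0.017 with only 80% planned power, so there is little slack. The nearest route to including state is the open-ended tail of the mixed-model covariate list. That applies only to knowledge over time, and it leaves the choice to be made after the data are seen.

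**Working it through.** **Inputs from section 5.0.** Difference of 5 points (30 vs 25), SD 15, 190 per arm, two-sided level 0.05/3 (written as 0.017). Screening rates 0.20 vs 0.35, 150 per arm, two-sided level 0.05.

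**Assumed input.** r, the share of outcome variance lying between states. The documents do not give it, nor the number of states or the patients per state. Values of 0, 2, 5 and 10% are shown. Balanced allocation within states is also assumed.

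**Step 1: reproduce the plan's power.** The t-test standard error is 15 × √(2/190) = 1.539, and 5/1.539 = 3.249. The critical value for 0.05/3 is z = 2.394. Power = Φ(3.249 − 2.394) = Φ(0.855) = 80.4% by normal approximation. The noncentral t gives 80.0% at 0.05/3 and 80.2% at 0.017. The stated 80% reproduces. The screening-rate figure also reproduces: 83.2% against the stated 83%.

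**Step 2: true standard error under stratified allocation.** True SE = 1.539 × √(1 − r). The t-test goes on estimating about 1.539, so the ratio of reported to true SE is 1/√(1 − r).

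**Step 3: size and power.**

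- True size of the t-test: 2Φ(−2.394/√(1 − r)).
- Power without state: Φ((5 − 2.394 × 1.539)/true SE).
- Power with state fitted: Φ(5/true SE − 2.394).

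| r (assumed) | True SE | Reported/true SE | True size | Power, state omitted | Power, state fitted | Gain (points) |
|---|---|---|---|---|---|---|
| 0% | 1.539 | 1.000 | 0.0167 | 80.4% | 80.4% | 0 |
| 2% | 1.524 | 1.010 | 0.0156 | 80.6% | 81.3% | 0.7 |
| 5% | 1.500 | 1.026 | 0.0140 | 81.0% | 82.6% | 1.6 |
| 10% | 1.460 | 1.054 | 0.0116 | 81.6% | 84.9% | 3.2 |

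Gains are taken before rounding. Power with state omitted also rises with r, because stratified allocation lowers the true variance whichever test is used. The proper comparison is therefore across a row, not against the nominal 80%.

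**Step 4: simulation.** The set-up was 10 states of 38 patients (assumed), permuted blocks of 4, level 0.017 and 6,000 replicates.

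- r = 5%: mean SE 1.538 without state and 1.499 with it; power 80.8% and 82.3%.
- r = 10%: mean SE 1.538 and 1.460; power 80.8% and 84.1%.

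These agree with the table on the SEs and, approximately, on the gains. The simulated null rejection rates are too noisy at this number of replicates to check the size column, which rests on the formula.

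**Step 5: screening rate.** The average rate is (0.20 + 0.35)/2 = 0.275, with variance 0.275 × 0.725 = 0.199. An assumed between-state SD of 5 points gives r = 0.0025/0.199 = 1.3% and an SE ratio of 1.006. An SD of 10 points gives r = 5.0% and a ratio of 1.026.

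**The case against.** The case for leaving the plan alone is a fair one. The error is in the safe direction: there is no bias and no excess of false positives, and the planned power is met. The t-test matches the sample-size calculation and avoids decisions about sparse states. The stated reason for stratifying reads as a precaution, not as evidence that states differ. The screening rate is exploratory. All of this stands, and it limits the weight of the point. It does not remove it: with no state effect, fitting 20 states (an assumed number) changes power only from 80.03% to 80.01%, so adjusting costs almost nothing and can only help materially.

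Three stronger readings are tempting, and the documents do not support them:

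- A reader might infer that the standard errors are wrong as planned. That depends on between-state variance, which the documents do not report. At r = 0 they are correct.
- A reader might infer that the stratification is wasted. It still balances the arms within states and still lowers the true variance. Only the credit for this in the standard error is lost.
- A reader might infer that every between-arm analysis is an unadjusted test. The plan also has a linear regression and a covariate-adjusted mixed model whose covariate list is open. The accurate statement is that none of them names state.

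Larger gains from adjusting for education, age or baseline knowledge are a separate matter. These are not stratification factors, and omitting them leaves the t-test's standard error valid.

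**Conclusion.** The point holds as a modest matter of efficiency and of consistency between design and analysis. The stratification factor is missing from the primary, knowledge and screening-rate tests. If states account for 2 to 10% of outcome variance, the primary standard errors are about 1.0 to 5.4% too wide, the 0.0167 tests run at about 0.0156 to 0.0116, and fitting state would add about 0.7 to 3.2 points of power. For the screening rate, the standard error would be about 0.6 to 2.6% too wide if state rates vary with an SD of 5 to 10 points. All these ranges rest on assumed between-state variation and on balanced allocation within states. The validity of the trial's conclusions is not in question.

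**What to change.** In the Analysis plan:

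1. Make the primary comparison of each of the three endpoints a linear model with arm and state. Do the same for the knowledge score and the knowledge change.
2. Set the rule for pooling low-enrolling states before the data are examined, for example pooling by quitline partner below a stated number of patients.
3. Use a Cochran-Mantel-Haenszel test stratified by state, with the same pooling, for the exploratory screening rate.
4. Name state among the mixed-model covariates.
5. Keep the two-group t-test as a sensitivity analysis.

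The sample size need not change, since the planned figures are met with or without state. State is already recorded for randomisation, so the cost is plan wording and the one decision on pooling.

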#### 1-week, 3-month, and 6-month Follow-up Assessments

When we enroll patients in the study we will schedule the 1-week follow-up (we allow up to 3 weeks after their scheduled follow-up to contact the patient). This is scheduled one week from the expected date of receipt of the intervention materials. If the patient did not receive the intervention materials, we re-send them and re-schedule the 1-week follow-up. The 3- and 6-month follow-ups are triggered by completion of prior follow-ups.

We will request contact information from patients at the time of enrollment. We will ask for names and contact information of additional persons who might be able to locate the patient if we cannot. During the 1-week follow-up assessment interview, we will administer the main outcome measures for the study (Preparation for Decision Making Scale, Decisional Conflict Scale), the secondary outcome measures (knowledge, screening intentions), and the measures of acceptability of the materials. See appendix M for the 1-week follow up survey. At the 3-month and 6-month follow-up assessments (we have up to three weeks after their scheduled follow-up date to contact the patients),

we will repeat the knowledge measure and ask about any use of lung cancer screening services. See appendices N and O for the 3-month and 6-month follow-up surveys, respectively.

If we are not able to complete the follow-up interviews by phone, we will mail a study questionnaire to the patient at the address they provide. Patients will receive \$50 after completion of the 1-week assessment and \$25 after completion of the 3-month assessment in the form of gift cards mailed to them (\$75 total). Patients asked to do the 6-month assessment will be mailed an additional \$25 gift card when they complete it. Subject compensation will be tracked in a log (see appendix P).

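### Secondary knowledge endpoint: the baseline knowledge subscale is used only in a change-score t-test; adjusting for it by ANCOVA would gain precision at no data cost

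*Combined protocol and SAP*

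**What the plan says.** Section 4.0 describes the baseline measurement: "The design includes a pre-test assessment with a subscale of the knowledge measure developed for this study". The section on follow-up assessments lists knowledge among the secondary outcomes at 1 week. For 3 and 6 months it says "we will repeat the knowledge measure and ask about any use of lung cancer screening services", with no mention of a subscale.

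The sample-size section powers knowledge on the scores themselves: "we will also compare the difference of knowledge scores between the two arms using two-sided two group t-test". It assumes 50 versus 55.75, SDs of 19.36 and 15.76, 380 participants and a two-sided alpha of 0.05, and states 88% power.

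The Analysis plan then contains three knowledge analyses:

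- a t-test on scores, parallel to the primary analysis ("We will perform similar analysis on knowledge scores");
- a t-test on change ("We will use two-sided two group t-test to compare the change of knowledge scores from baseline to post intervention between the two arms");
- a linear mixed model over the 1-week, 3-month and 6-month assessments, whose named covariates are arm, age, gender, race, education and insurance, plus unspecified others.

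No analysis is described that adjusts the post-intervention score for baseline knowledge.

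**The concern.** A baseline measure of the outcome is often the most useful covariate a trial has. Here it is collected, but its only named use is subtraction. A change score fixes the weight on baseline at one, whatever the data say. If the correlation with the follow-up score is modest, subtraction adds more noise than it removes, and the test can be weaker than one that ignores baseline. ANCOVA estimates the weight instead.

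The baseline holds only a subscale, which strengthens the case. A change score needs the same items at both times, so a coherent one covers a narrower outcome than the one powered. ANCOVA needs no common scale, and the subscale can serve directly as a covariate for the full score.

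At stake is precision on knowledge, the one outcome beyond the three primary ones for which Section 2.0 states a directional hypothesis.

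**Working it through.** **Inputs from the sample-size section.** Control SD 19.36; decision-aid SD 15.76; difference 5.75; 190 per arm; two-sided alpha 0.05. (That section writes Aim 1 and Aim 2, read here as Arm 1 and Arm 2.)

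**Inputs assumed.** The documents do not give the within-arm baseline-to-post correlation r or the ratio k = baseline SD / post SD. Both are varied. The 5.75-point effect and one average post SD are also assumed to apply to every analysis compared.

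**Step 1: reproduce the plan's figure.** Average SD s = √[(15.76² + 19.36²)/2] = 17.65. Standard error = 17.65 × √(2/190) = 1.811. Noncentrality = 5.75/1.811 = 3.17. The unequal-variance t-test has 88.6% power, so the stated 88% is confirmed for the t-test on scores.

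**Step 2: SD for each analysis.**

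- Post score: s
- Change score: s√(1 + k² − 2rk)
- ANCOVA residual: s√(1 − r²)

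Change is more precise than the post score only if r > k/2. The change variance minus the ANCOVA variance is s²[(1 + k² − 2rk) − (1 − r²)] = s²(k − r)². This is never negative, and it is zero only when r = k. ANCOVA is therefore at least as precise as either t-test, apart from the few degrees of freedom spent on covariates.

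**Step 3: power at k = 1, 190 per arm.** The unadjusted score t-test stays at 88.6% throughout.

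| r | SD of change | Power, change | ANCOVA SD | Power, ANCOVA |
|---|---|---|---|---|
| 0.2 | 22.33 | 70.7% | 17.30 | 89.8% |
| 0.3 | 20.89 | 76.3% | 16.84 | 91.3% |
| 0.4 | 19.34 | 82.4% | 16.18 | 93.3% |
| 0.5 | 17.65 | 88.6% | 15.29 | 95.5% |
| 0.7 | 13.67 | 98.3% | 12.61 | 99.3% |

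**Step 4: sensitivity to k at r = 0.3.** ANCOVA power is 91.3% in every row, because it does not depend on k.

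| k | SD of change | Power, change |
|---|---|---|
| 0.5 | 17.21 | 90.1% |
| 0.75 | 18.62 | 85.1% |
| 1 | 20.89 | 76.3% |
| 1.25 | 23.76 | 65.3% |

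The ANCOVA advantage over the change score at r = 0.3 thus runs from about 1 percentage point (k = 0.5) to 26 (k = 1.25). The ANCOVA figures take the covariate to be the baseline subscale alone; any gain from adjusting for state is not counted.

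**The case against.** The strongest reply is that nothing in the plan is invalid. The powered t-test on scores is kept, its 88% is right, and the change test is an additional analysis with no power claim attached. Under randomisation both t-tests give valid between-arm comparisons. All of this stands, and it makes the point an efficiency gain rather than the correction of an error.

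The size of the loss is also open to challenge. Section 1.0 reports that patients know very little about lung cancer screening. That might suggest a low correlation, but a floor at baseline could equally shrink the baseline SD and so reduce the loss. At k = 1 and r above 0.5, change beats the unadjusted score test. The size of any loss cannot be fixed from the documents. What the reply does not remove is that ANCOVA does at least as well across the whole range.

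Three stronger readings are tempting but unsupported:

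- **The plan subtracts a subscale score from a full score.** No text says so. Item content and scoring may be set out in the survey appendices, which are not available here. Which items enter the change score is a missing detail, not a demonstrated mistake.
- **Knowledge is tested three times, each at 0.05.** An alpha is stated only for the score t-test; none is given for the change test or the mixed model.
- **The knowledge hypothesis lacks its stated power.** The score t-test has that power. It is also the only knowledge analysis with a sample-size justification, which makes it the lead in practice although the plan does not use the word.

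**Conclusion.** The point holds as a free improvement to a secondary endpoint. The baseline subscale is collected but is not used as a covariate in any named analysis, and the change-score t-test is the less efficient way to use it. The 88% applies to the score t-test and cannot be quoted for the change test.

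Compared with the unadjusted score t-test, ANCOVA raises power from 88.6% to between 89.8% (r = 0.2) and 99.3% (r = 0.7). Compared with the change test, the gain at k = 1 runs from 19 percentage points at r = 0.2 to 1 point at r = 0.7. These sizes rest on assumed values of r and k, and on carrying the full-score effect and SD over to a change score that may cover fewer items. The ordering of the methods does not depend on particular values of r or k; the magnitude does.

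The three primary endpoints and the sample size are not affected.

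**What to change.** In the Analysis plan, make the main knowledge analysis one ANCOVA: full 1-week knowledge score on arm, with the baseline subscale score and state as covariates. State belongs in the model because randomisation is stratified by it. This replaces the change-score t-test and the unadjusted score t-test; the latter may be kept as a labelled sensitivity analysis. Report any change score descriptively, using only items asked at both times. The sample-size paragraph can stand, since its 88% describes the unadjusted score test and is conservative for the ANCOVA if baseline and follow-up scores are correlated.

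The cost is a wording change made before the data are analysed. It needs no new data, participants or assessments.
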